5.2 Selection of Study Population

It is anticipated that approximately 855 subjects with active moderate to severe CD will be enrolled at approximately 400 sites worldwide. Both non-bio-IR and bio-IR subjects will be included. The bio-IR population will be a minimum of approximately 540 subjects and the non-bio-IR population will be a minimum of approximately 315 subjects.

A subject may be enrolled in this study provided that he/she has met all of the inclusion criteria and none of the exclusion criteria specified in this protocol.

5.2.1 Inclusion Criteria

1. Male or female aged ≥ 18 to ≤ 80 years, or minimum age of adult consent according to local regulations, at the Baseline Visit. Where locally permissible, subjects 16 to < 18 years of age who meet the definition of Tanner stage 5 for development (refer to [Appendix J](#)) at the Baseline Visit (sites will be notified when adolescents may enroll).
2. Confirmed diagnosis of CD for at least 3 months prior to Baseline. Appropriate documentation of biopsy results consistent with the diagnosis of CD, in the assessment of the Investigator, must be available.
3. Crohn's disease activity index (CDAI) score 220 – 450 at Baseline.
4. Endoscopic evidence of mucosal inflammation as documented by the SES-CD of ≥ 3 . All eligible scores exclude the presence of narrowing component and are confirmed by a central reader. (Once cap of no more than 85 subjects is reached, enrollment criterion will be an SES-CD of ≥ 6 for ileocolonic or colonic disease or SES-CD of ≥ 4 for isolated ileal disease.)
5. Average daily SF ≥ 4 and/or average daily AP score ≥ 2 at Baseline.
6. Demonstrated intolerance or inadequate response to one or more of the following categories of drugs: aminosalicylates, oral locally acting steroids, systemic steroids (prednisone or equivalent), immunomodulators, and/or biologic therapies
 - Demonstration of intolerance requires no minimum dose or duration of use (intolerance includes patients with a known TPMT genetic mutation or low activity).
 - Inadequate response is defined as outlined below:
 - Oral aminosalicylates (e.g., mesalamine, sulfasalazine, olsalazine, balsalazide):

- Signs and symptoms of persistently active disease, in the opinion of the Investigator, during a current or prior course of at least 4 weeks of treatment with 2.4 g/day mesalamine, 4 g/day sulfasalazine, 1 g/day olsalazine, or 6.75 g/day balsalazide,
- Oral locally acting steroids (e.g., budesonide, beclomethasone):
 - Signs and symptoms of persistently active disease in the opinion of the Investigator, during or after a course of at least 4 weeks of treatment with 9 mg/day budesonide or 5 mg/day beclomethasone,
 - or
 - Inability to taper oral budesonide to at or below 6 mg/day without recurrent active disease,
- IV or Oral systemic steroids (prednisone or equivalent):
 - Signs and symptoms of persistently active disease in the opinion of the Investigator, during or after tapering of at least one regimen consisting of a dose equivalent to prednisone ≥ 40 mg/day orally for 3 weeks or intravenously for 1 week,
 - or
 - Inability to taper oral systemic steroids at or below a dose equivalent to prednisone 10 mg/day without recurrent active disease,
- Immunomodulators:
 - Signs and symptoms of persistently active disease in the opinion of the Investigator, during a current or prior course of at least 90 days of treatment with one or more of the following:
 - AZA: ≥ 2.0 mg/kg/day rounded to the nearest available tablet or half tablet formulation (≥ 1 mg/kg/day for subjects in Japan, Korea, Hong Kong, Taiwan, Singapore, or China) (or a documented 6-TGN level of ≥ 230 pmol/ 8×10^8 RBC)
 - 6-MP: ≥ 1 mg/kg/day rounded to the nearest available tablet or half tablet formulation (≥ 0.6 mg/kg/day for subjects in Japan, Korea, Hong Kong, Taiwan, Singapore, or China) (or a 6 TGN level of ≥ 230 pmol/ 8×10^8 RBC)
 - MTX: ≥ 15 mg/week subcutaneous (SC) or intramuscular (IM)

- *Note:* Oral MTX use is allowed during the study, however prior or current use of oral MTX is not sufficient for inclusion into the study
 - Biologic therapies for CD:
 - Signs and symptoms of persistently (in the opinion of the Investigator) active disease despite a history of one or more of the following:
 - At least one 6-week induction regimen of infliximab (≥ 5 mg/kg IV at Weeks 0, 2, and 6),
 - At least one 4-week induction regimen of adalimumab (one 160 mg SC dose at Week 0, followed by one 80 mg SC dose at Week 2 [or one 80 mg SC dose at Week 0, followed by one 40 mg SC dose at Week 2, in countries where this dosing regimen is approved]),
 - At least one 4-week induction regimen of certolizumab pegol (400 mg SC at Weeks 0, 2, and 4),
 - At least one 6-week induction regimen of vedolizumab (300 mg IV at Weeks 0, 2, and 6),
 - At least one 12-week induction regimen of natalizumab (300 mg IV every 4 weeks)
 - At least one 8-week induction regimen of ustekinumab [260 mg (≤ 55 kg) or 390 mg (> 55 to ≤ 85 kg) or 520 mg (> 85 kg) IV, followed by 90 mg SC at Week 8] (Once cap of no more than 20% ustekinumab exposed subjects is reached, subjects with prior ustekinumab exposure will not be allowed to enroll.)
 - Recurrence of symptoms during scheduled maintenance dosing following prior clinical benefit of the above biologics
 - *Note:* Subjects who discontinued biologics for reasons other than inadequate response as defined above or intolerance (e.g., change of insurance) must meet the criteria for intolerance or inadequate response to aminosalicylates, oral locally acting steroids, systemic steroids (prednisone or equivalent), and/or immunomodulators as defined above
7. If female, subject must meet the criteria as stated in Section 5.2.4 of this protocol *Contraception Recommendations*. Females of childbearing potential must have a

negative serum pregnancy test result during Screening, and a negative urine pregnancy at Baseline. Females of non-childbearing potential (either postmenopausal or permanently surgically sterile as defined in Section 5.2.4) during Screening do not require pregnancy testing at Baseline.

Note: Subjects with borderline serum pregnancy test at Screening must have a serum pregnancy test ≥ 3 days later to document continued lack of a positive result.

8. Subject must be able and willing to give written informed consent and to comply with the requirements of this study protocol. In Japan, if the subject is < 20 years old, a subject's parent or legal guardian must be willing to give written informed consent.

Rationale for Inclusion Criteria

- 1 – 6 To select the adequate subject population with a disease status representative of the target population for evaluation
- 7 The impact of risankizumab on pregnancy and reproduction is unknown
- 8 In accordance with harmonized Good Clinical Practice (GCP)

5.2.2 Exclusion Criteria

1. Subject with a current diagnosis of ulcerative colitis or indeterminate colitis.

Concomitant Medications and Treatments

2. Subject on CD-related antibiotics who has not been on stable doses for greater than, or discontinued within, 14 days prior to Baseline.
3. Subject on oral aminosalicylates who has not been on stable doses for greater than, or discontinued within, at least 14 days prior to Baseline.
4. Subject taking oral corticosteroids:
 - Budesonide > 9 mg/day
 - Beclomethasone > 5 mg/day

- Prednisone or equivalent > 20 mg/day
 - Or has not been on the current course for ≥ 14 days prior to Baseline and on a stable dose for ≥ 7 days prior to Baseline
5. Subject on immunomodulators (AZA, 6-MP, MTX) who:
- Has not been on the current course for ≥ 42 days prior to Baseline, and
 - Has not been on a stable dose for ≥ 35 days prior to Baseline

Medications and Treatments **During** the Screening Period

6. Subject who received IV anti-infectives within 35 days prior to Baseline visit or oral/intramuscular anti-infectives (non-CD-related) within 14 days prior to the Baseline visit. This does not apply to TB prophylaxis.
7. Subject who received exclusive enteral nutrition or any parenteral nutrition within 35 days prior to Baseline.
8. Subject who received any live bacterial or viral vaccination within 30 days (8 weeks for Japan) prior to Screening or during the Screening Period.
9. Subject who received cyclosporine, tacrolimus, or mycophenolate mofetil within 35 days prior to Baseline.
10. Subject who received fecal microbial transplantation within 35 days prior to Baseline.

Prior Medications and Treatments

11. Subject who received any:
- approved biologic agent: infliximab, adalimumab, certolizumab, vedolizumab, natalizumab within 8 weeks prior to Baseline or ustekinumab within 12 weeks prior to Baseline, or
- Note: If there is proper documentation of an undetectable drug level measured by a commercially available assay for any of the approved biologics above, there is no minimum washout prior to Baseline.
- any investigational biologic or other agent or procedure within 35 days or 5 half-lives prior to Baseline, whichever is longer.

12. Subject with prior exposure to p19 inhibitors (e.g., risankizumab)
13. Subject has been taking combination of two or more of the following: oral budesonide, or oral beclomethasone and/or oral prednisone (or equivalent) simultaneously, with the exception of inhalers, within 14 days prior to Screening or during the Screening period.
14. Subject who received IV/intramuscular corticosteroids within 14 days prior to Screening or during the Screening period.
15. Subject who received therapeutic enema or suppository, other than required for endoscopy, within 14 days prior to endoscopy used for Screening or during the Screening period.
16. Subject who received apheresis (e.g., Adacolumn apheresis) \leq 60 days prior to Screening or during the Screening period.
17. Subject who has concomitant cannabis use either recreational or for medical reasons within 14 days of Baseline or any history of clinically significant drug, or alcohol abuse in the last 12 months.

CD Related

18. Subject with currently known complications of CD such as:
 - abscess (abdominal or perianal),
 - symptomatic bowel strictures,
 - > 2 missing segments of the following 5 segments: terminal ileum, right colon, transverse colon, sigmoid and left colon, and rectum
 - fulminant colitis,
 - toxic megacolon,
 - or any other manifestation that might require surgery while enrolled in the study.
19. Subject with ostomy or ileoanal pouch.
20. Subject diagnosed with short gut or short bowel syndrome.

21. Subject with surgical bowel resection within the past 3 months prior to Baseline, or a history of ≥ 3 bowel resections.

Safety

22. Subject who has a known hypersensitivity to risankizumab or the excipients of any of the study drugs or the ingredients of Chinese hamster ovary (CHO).
23. Subjects with the following chronic or active infections:
- Active, chronic, or recurrent infection that based on the Investigator's clinical assessment makes the subject unsuitable candidate for the study,
 - Infection with *C. difficile* toxin or other intestinal pathogen during Screening,
 - Are infected with human immunodeficiency virus (HIV),
 - QuantiFERON[®]-TB test or Purified Protein Derivative (PPD) skin test, or both, according to local guidelines, will be performed during Screening. QuantiFERON[®]-TB test is preferred for subjects who received Bacillus Calmette-Guérin (BCG) vaccination or were exposed to other Mycobacteria species. Subjects with a positive test result (or indeterminate results that have been repeated) may participate in the study if further work up (according to local practice/guidelines) establishes conclusively that the subject has no evidence of active tuberculosis. Subjects with a history of active TB who have documented completion of a full course of anti-TB therapy may be allowed to enter the study after consultation with the AbbVie TA MD. If latent TB is established, TB prophylaxis/treatment should be initiated and maintained according to local country guidelines.
 - Have active hepatitis B or hepatitis C defined as:
 - HBV: hepatitis B surface antigen (HBs Ag) positive (+), or detected sensitivity on the HBV deoxyribonucleic acid (DNA) polymerase chain reaction (PCR) qualitative test for hepatitis B core antibody (HBc Ab) positive subjects;
 - HCV: HCV ribonucleic acid (RNA) detectable in any subject with positive anti-HCV antibody (HCV Ab)

24. Subject with a previous history of dysplasia of the gastrointestinal tract or found to have dysplasia, other than completely removed low-grade dysplastic lesions, in any biopsy performed during the Screening endoscopy.
25. Subject with a known history of lymphoproliferative disease, including lymphoma, or signs and symptoms suggestive of possible lymphoproliferative disease, such as lymphadenopathy and/or splenomegaly.
26. Subject with current or previous history of malignancy other than a successfully treated non-metastatic cutaneous squamous cell or basal cell carcinoma or localized carcinoma in situ of the cervix.
27. Subject who has severe, progressive, or uncontrolled renal, hepatic, hematological, endocrine, disorder or symptoms thereof.
28. Female subjects who is pregnant, breastfeeding, or is considering becoming pregnant during the study or for approximately 140 days after the last dose of study drug.
29. Subject who has any condition, including any physical, psychological, or psychiatric condition, which in the opinion of the Investigator, would compromise the safety of the subject or the quality of the data and renders the subject an unsuitable candidate for the study.
30. Screening laboratory and other analyses show any of the following abnormal results:
 - Aspartate transaminase (AST), alanine transaminase (ALT) $> 2 \times$ upper limit of the reference range;
 - White blood cell (WBC) count $< 3.0 \times 10^9/L$;
 - Total bilirubin ≥ 2 mg/dL; except for subjects with isolated elevation of indirect bilirubin relating to Gilbert syndrome;
 - Estimated glomerular filtration rate by simplified 4-variable Modification of Diet in Renal Disease (MDRD) formula < 30 ml/min/1.73 m².
 - Hemoglobin < 8 g/dL

- Platelets < 100,000/ μ L
- Positive serum pregnancy test at the Screening visit or positive urine pregnancy test at the Baseline visit.

Laboratory values can be re-tested once during the screening period after discussion and clearance with the TA MD. If the re-tested lab value(s) remain(s) exclusionary, the subject will be considered a screen failure. Redrawing samples if previous samples were unable to be analyzed would not count as a retest since the previous result was never obtained

31. No known active COVID-19 infection. Subject must not have signs/symptoms associated with COVID-19 infection.

Subjects who do not meet COVID-19 eligibility criteria must be screen failed and may only rescreen after they meet the following COVID-19 viral clearance criteria:

- Symptomatic subjects: At least 2 negative viral tests in a row completed locally, \geq 24 hours apart after at least 10 days have passed since recovery, defined as resolution of fever without use of antipyretics and improvement in respiratory symptoms (e.g., cough, shortness of breath)
- Asymptomatic subjects: At least 2 negative viral tests in a row completed locally, \geq 24 hours apart after at least 10 days have passed since prior positive result (Note: subjects who develop symptoms will follow guidance above for symptomatic subjects)

Frequency or timing of COVID-19 testing and interval between testing for the above viral clearance criteria may be adjusted to account for epidemiological trends, updated information regarding infectivity and local/institutional guidelines.

Rationale for Exclusion Criteria

- | | |
|--------|--|
| 1 | To avoid medical conditions that may compromise the ability to identify subjects with the correct diagnosis or to interpret medical importance of clinical results |
| 2 – 17 | To avoid bias for the evaluation of efficacy and safety by concomitant use of other medications or treatments and to ensure the safety of the subject |

- 18 – 21 To avoid complications of CD that may compromise the evaluations of efficacy and safety
- 22 – 31 To ensure the safety of the subject and or others

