- If the baseline urine pregnancy test performed at the site is negative, then dosing with study drug may begin. If the baseline urine pregnancy test performed at the site is positive, dosing with study drug must be withheld and a serum pregnancy test is required. The serum pregnancy test will be sent to and performed by the central laboratory. If the serum pregnancy test is negative, study drug may be started. If the serum pregnancy test is positive, study drug must be withheld and the subject must be discontinued from the study. In the event a pregnancy test result is borderline, a repeat test is required.
- If a urine pregnancy test post-baseline is positive, study drug will be temporarily discontinued and a serum pregnancy test is required. The serum pregnancy test will be sent to and performed by the central laboratory. If the serum pregnancy test is negative, study drug may be restarted. If the serum pregnancy test is positive, study drug will be permanently discontinued.

A pregnant or breastfeeding female will not be eligible for participation or continuation in this study or be allowed to continue study drug.

High-Sensitivity C-Reactive Protein (hs-CRP)

Blood samples for hs-CRP will be obtained per [Appendix C](#). The hs-CRP results will remain blinded to Investigator, study site personnel and the subject.

Blood draws should be performed, as much as possible, after all efficacy assessments, questionnaires (CDAI, IBDQ, etc.), and vital sign determinations are obtained and before study drug administration during a visit. In order to maintain the study blind, local laboratory testing for hs-CRP for routine subject monitoring should not be performed.

Crohn's Disease Activity Index (CDAI)

Average daily SF, average daily AP score, and well-being will be calculated from the subject diary. During screening subjects will be instructed on how to calculate the number of very soft and liquid stools, including a visual depiction. Physical exam and appropriate laboratory values will be calculated at all study visits beginning at Baseline. The Screening period will be a minimum of 7 days to calculate the Baseline scores.

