Intravenous and SC study drug will be administered to all subjects on-site. For WOCBP subjects, the urine pregnancy test needs to be negative prior to receiving study drug. The site will be provided administration instructions. Also, the initial 20 subjects enrolled between the Phase 3 induction trials will be monitored on site for 2 hours after completion of each infusion. Subjects should be observed after study drug administration until judged clinically stable by the study personnel. If an anaphylactic reaction or other serious allergic reaction occurs, administration of study drug should be discontinued immediately, appropriate laboratory testing samples drawn and appropriate therapy initiated.

Study drug kits are assigned by the IRT following the subjects randomized treatment schedule. (Refer to Section 5.5 for additional information).

During the Study Drug Dosing Period, a subject with confirmed (viral test positive) or suspected COVID-19 infection can only be dosed with study drug if the following COVID-19 viral clearance criteria are met:

- Symptomatic subjects: At least 2 negative viral tests in a row, ≥ 24 hours apart after at least 10 days have passed since recovery, defined as resolution of fever without use of antipyretics and improvement in respiratory symptoms (e.g., cough, shortness of breath)
- Asymptomatic subjects: At least 2 negative viral tests in a row, ≥ 24 hours apart after at least 10 days have passed since prior positive result (note:

subjects who develop symptoms will follow guidance above for symptomatic subjects)

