- k. For Japan only: for subjects with HBs Ab (+) and/or HBc Ab (+) at Screening, the HBV-DNA PCR test should be performed again at Week 12 and Week 24. Retesting at Week 12 and Week 24 is not necessary with subjects that have a history of HBV vaccine and are HBs Ab (+).
- l. HIV testing will be performed at the central laboratory, which will report the results directly to the sites. AbbVie will not receive results from the testing.
- m. Dipstick urinalysis will be completed by the sites at required visits. A microscopic analysis will be performed by the central laboratory, in the event the dipstick results show leukocytes, nitrite, protein, ketones or blood greater than negative or glucose greater than normal.
- n. Urinalysis, chemistry and hematology, hs-CRP, and FCP may be collected at other scheduled and unscheduled visits than indicated in the table if they are warranted by the Investigator.
- o. Lab assessments will only need to be repeated at Baseline if the time between Screening and Baseline is greater than 14 days, or if the subject's health status has changed to warrant a repeat test.

- p. Serum pregnancy test will be performed on all WOCBP at Screening. Urine pregnancy test will be performed locally as indicated in the table for all WOCBP. The urine pregnancy test must be negative to receive study drug. If any urine pregnancy test is positive, a serum pregnancy test will be performed by the central laboratory. FSH will be performed in all female subjects < 55 years old with no menses for 12 months.
- q. Serum risankizumab concentrations and ADA will be determined from samples collected just prior to dosing at every visit. The date and time of sample collection will be captured on the eCRF. If the subject consented to the optional intensive PK sampling, refer to [Appendix H](#).
- r. Stool sample will be collected at each time point indicated in the table. For the visit when endoscopy will be conducted, stool sample should be collected prior to bowel prep and should be returned to the site per the instructions provided outside of this protocol. If a sample cannot be obtained during the site visit, the site will give instructions and a stool sample supply kit.
- s. Subjects should also be dispensed the patient information card.

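### For a woman with a positive Baseline urine pregnancy test and a negative central serum test, the eligibility criteria exclude her while Section 5.3.1.1 lets study drug start

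*Protocol*

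**What the plan says.** All references are to the current protocol text, not to its list of changes.

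- **Section 5.2.1, inclusion 7.** Women of childbearing potential need a "negative serum pregnancy test result during Screening, and a negative urine pregnancy at Baseline".
- **Section 5.2.2, exclusion 30.** The exclusionary results include "Positive serum pregnancy test at the Screening visit or positive urine pregnancy test at the Baseline visit". The criterion closes with a retest provision: "Laboratory values can be re-tested once during the screening period after discussion and clearance with the TA MD".
- **Section 1.2, synopsis.** Both criteria are repeated.
- **Section 5.3.1.1, Pregnancy Testing.** After a positive urine test at Baseline, "dosing with study drug must be withheld and a serum pregnancy test is required", and the sample goes to the central laboratory. Then: "If the serum pregnancy test is negative, study drug may be started". A positive serum result means no drug and the end of participation. After Baseline, a positive urine test interrupts drug; a negative serum result allows it to restart and a positive one ends it for good.
- **Section 5.3.1.1, Study Drug Dispensing/Administration.** "For WOCBP subjects, the urine pregnancy test needs to be negative prior to receiving study drug".
- **Appendix C, note p.** "The urine pregnancy test must be negative to receive study drug". The note then calls for a central serum test after any positive urine test, but does not say what follows if that serum test is negative.

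**The concern.** One set of provisions decides on the urine result alone. Another treats the urine result as provisional and decides on the central serum result. The two agree for every combination of results except urine positive with serum negative, where they point in opposite directions.

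The gate comes before the first dose. The protocol justifies inclusion 7 by saying that the drug's effect on pregnancy and reproduction is not known, and gives subject safety as the reason for exclusions 22 to 31. With about 400 sites (Section 5.2), staff will meet this case separately and have no text to tell them which rule takes precedence. A site that follows Pregnancy Testing enrols a woman who fails an inclusion criterion and meets an exclusion criterion, although Section 7.0 rules out intentional deviations except to remove an immediate hazard. A site that follows the criteria screen-fails a woman whom the procedure section would allow to be dosed.

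**Working it through.** The protocol states no figure to reproduce on this point. The check is to take one subject through each provision, then to look for a sentence that reconciles them.

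**Step 1: the subject.** A woman of childbearing potential, serum negative at Screening, urine positive at Baseline, follow-up central serum negative.

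| Provision | Deciding test | Outcome |
|---|---|---|
| Inclusion 7 (and synopsis) | Baseline urine | Not met: ineligible |
| Exclusion 30 (and synopsis) | Baseline urine | Met: ineligible |
| 5.3.1.1, Study Drug Dispensing/Administration | Urine | No drug on this result |
| Appendix C, note p | Urine, with reflex serum | No drug on this result; consequence of a negative serum not stated |
| 5.3.1.1, Pregnancy Testing | Central serum | Drug may start |

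Section 5.3.1.1 is therefore at odds with Sections 5.2.1 and 5.2.2, and two of its own subsections are at odds with each other.

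**Step 2: is there a reconciling sentence?** The retest provision in exclusion 30 is the only candidate. It covers laboratory values, once, in the screening period, after clearance by the sponsor's medical director. The case here is a local urine test at Baseline followed by a different, central test, and Pregnancy Testing mentions no such clearance. The provision does not settle the matter. Elsewhere the protocol writes its exceptions out: exclusion 30 exempts Gilbert syndrome from the bilirubin limit, and inclusion 7 carries a note on borderline serum results that agrees with Pregnancy Testing. Neither criterion has an exception for urine positive with serum negative.

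**Step 3: after Baseline.** Inclusion 7 and exclusion 30 no longer apply. Pregnancy Testing allows restart on a negative serum result, while the administration text and note p still ask for a negative urine test before drug. The conflict remains but is narrower: an explicit algorithm against two short statements.

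**Step 4: how many subjects.** The protocol gives neither the share of women of childbearing potential nor the urine false-positive rate. Assume 35% to 45% and 0.1% to 1% per test.

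- Maximum enrolment (Sections 1.2 and 5.1): 855 + 85 = 940.
- Women of childbearing potential: 940 × 0.35 = 329 to 940 × 0.45 = 423.
- Urine positive, serum negative at Baseline: 329 × 0.001 = 0.3 to 423 × 0.01 = 4.2.

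The range rests wholly on those two assumptions. Later visits would add to it; that addition is not estimated here.

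**Step 5: randomisation.** Sections 5.1 and 5.5.3 randomise only subjects who meet all inclusion and no exclusion criteria, so eligibility comes first in principle. If the deciding test is a central serum result, eligibility cannot be settled until it is reported, and the protocol does not say that the randomisation call waits for it. A subject randomised in the meantime and then never dosed would fall outside the ITT set, which requires at least one dose (Section 8.1.1.1).

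**The case against.** The best defence is that the short statements give the default gate and Pregnancy Testing gives the detailed handling of a positive: withhold, confirm, decide. Note p supports this, since it orders a serum test itself. That is a fair reading of the administration text and of note p, and it weakens the conflict after Baseline. It does not reach inclusion 7 and exclusion 30, which turn on the Baseline urine result and contain no exception for a negative serum test.

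Several stronger readings are tempting, and the protocol does not support them.

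- *One site could both dose and screen-fail the same woman.* It could not; a site does one or the other. The inconsistency is between sites.
- *Appendix C excludes her.* Note p is a condition for receiving drug, not an eligibility criterion.
- *A pregnant woman could be dosed.* No reading allows drug after a positive serum test. Pregnancy Testing bars pregnant women from participation and from drug, and exclusion 28 excludes pregnancy independently.
- *A serum-positive woman at Baseline is handled in conflicting ways.* Pregnancy Testing calls her discontinued where the criteria would make her a screen failure. That is a disposition label; either way she gets no drug.
- *Randomisation precedes eligibility.* Sections 5.1 and 5.5.3 say otherwise. Only the wait for a central result is left unstated.

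**Conclusion.** The point holds as a contradiction in the current text. For a urine-positive, serum-negative woman at Baseline, inclusion 7 and exclusion 30 make her ineligible and Pregnancy Testing says drug may start. The administration text and note p add a lesser conflict, at Baseline and at restart. No sentence states precedence.

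The consequence is that like subjects may be treated differently across sites, with an eligibility deviation wherever Pregnancy Testing is followed. That the conflict exists rests on the wording alone. Its size, 0.3 to 4 subjects at Baseline out of at most 940, rests on the assumed rates. A reader might infer a threat to the efficacy result; at this size there is none, and sample size, power and alpha are unaffected. It is worth correcting because it governs enrolment and dosing at a safety gate and the correction is cheap.

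**What to change.** Reconcile inclusion 7, exclusion 30, Pregnancy Testing and Study Drug Dispensing/Administration in Section 5.3.1.1, Appendix C note p, and the synopsis to a single rule for the subject with a positive urine and a negative central serum test. Use the same words in each place, and say whether the rule also governs restart after a post-baseline positive urine test. Add that the IRT randomisation call is not made until the test on which the rule relies has been reported. Which rule applies is a clinical decision for the sponsor's medical team.

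The cost is wording in five places plus the synopsis. No new test is needed, because the central serum test is already specified.
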